**Overall Design:**

Phase 1b, multicenter, randomized, double-blind, placebo-controlled, crossover study

**Brief Summary:**

The purpose of this study is to investigate the effects of oral administration of 1 mg/day V117957 each evening in female subjects with overactive bladder syndrome as compared to placebo. The study will consist of a Screening/ Washout Period (up to 4 weeks), Single-blind Placebo Run-in Period (2 weeks), Double-blind Treatment Period (8 weeks), Single-blind Placebo Washout Period (1 week), and Follow-up Period (up to 1 week).

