**Number of Participants:**

It is estimated that up to 150 subjects will be screened to yield approximately 75 subjects that will enter Single-blind Run-in Period to yield approximately 44 subjects that will enter the Double-blind Treatment Period. A sample size of 38 completers will have 81% power to detect a treatment difference in means of numbers of micturition per 24 hours of 0.5, assuming a standard deviation of differences of 1.4, using a paired t-test with a 10% one-sided significance level. Assuming a 15% dropout rate, a sample size of 44 would be needed.

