**Treatment Groups and Duration:**

V117957 (6-weeks) and Placebo (5-weeks).

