**Schema:**

Phase	Pre-randomization		Post-randomization										Single-blind washout	Follow-up
	Screening / washout	Single-blind Run-in	Double-blind Treatment											
Day	-42 to -16	-15	-1 A	1	14	15	28	35	42	49	56	63	70	
Clinic Visit	V1	V2	V3 A		V4		V5		V6		V7	V8	V9	
Phone call B				P1		P2		P3		P4				
Tx Sequence A		Placebo		Placebo	V117957								Placebo	
Tx Sequence B		Placebo		V117957						Placebo	Placebo			

A Visit 3, Day -1, is end of Single-blind Run-in Period and start of the Double-blind Treatment Period. At visit 3, a subject that has met all inclusion/exclusion criteria, has met all randomization eligibility criteria, and has completed all study procedures, will be dispensed double-blind study-drug with instruction to ingest first dose that evening 30 minutes before bedtime.

B Phone contact between clinic visits to assess tolerability and review diary/dosing instructions.

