**Table 2. Schedule of Assessments: Post-randomization Phase**

*C-SSRS=Columbia-Suicide Severity Rating Scale; ECG=Electrocardiogram; ESS= Epworth Sleepiness Scale; EOS= End of Study; EOT= End of Treatment; ET= Early Termination; OAB-q LF= Overactive Bladder Questionnaire long form; P=Phone; PPBC= Patient Perception of Bladder Condition; PPIUS= Patient Perception of Intensity of Urgency Scale; SGRA=Subject Global Response Assessment; SISO= Symptom Impact on Sleep Questionnaire; V=Visit.*

A Visit window is  $\pm 1$  day.

B Visit 3, Day -1, is end of Single-blind Run-in Period and start of the Double-blind Treatment Period. At visit 3, a subject that has met all inclusion/exclusion criteria, has met all randomization eligibility criteria, and has completed all study procedures, will be dispensed double-blind study-drug with instruction to ingest first dose that evening 30 minutes before bedtime.

c May be phone call instead of clinic visit if no safety issue identified.

D Phone contact between clinic visits to assess tolerability and review diary/dosing instructions.

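### Both sequences are on V117957 from about Day 15 to Day 42, so current treatment is predictable from the schema for half of the double-blind period; the paired comparison should rest on V4 and V7

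*Combined protocol and SAP*

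**What the plan says.** The Overall Design line calls the trial a "Phase 1b, multicenter, randomized, double-blind, placebo-controlled, crossover study". The Brief Summary lists a "Single-blind Placebo Run-in Period (2 weeks"), followed by the "Double-blind Treatment Period (8 weeks), Single-blind Placebo Washout Period (1 week"). Treatment Groups and Duration gives each subject's exposure as "V117957 (6-weeks) and Placebo (5-weeks").

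The Schema shows Sequence A taking placebo and then V117957 after randomization, and Sequence B taking V117957 and then placebo. Clinic visits V4, V5, V6 and V7 stand under Days 14, 28, 42 and 56. Staff also telephone subjects between visits. The footnote gives the purpose: "Phone contact between clinic visits to assess tolerability and review diary/dosing instructions".

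Section 1.4.1 summarises efficacy by treatment group at each scheduled time point. It tests V117957 against placebo on each subject's difference between the two periods, but does not name the visits that supply the two values. Section 1.4.3 summarises treatment-emergent adverse events by treatment group. Nothing in the text provided mentions a stretch in which both sequences receive the same treatment.

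**The concern.** A double blind protects a comparison when those who treat, question and report cannot tell which treatment a subject is on. In a stretch where both sequences give the same drug, the random code hides nothing about current treatment. A site member with the schema needs no code break at V5 or V6.

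Two features make this worth raising.

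- **It is one-sided.** Within the double-blind period, the predictable weeks are all V117957 weeks. If knowledge of treatment affects diary coaching, the clinic questionnaires, or how adverse events are elicited and attributed, it affects V117957 data and not double-blind placebo data. Such an effect would not cancel in a within-subject difference that uses a value from that window.
- **There is no concurrent placebo.** By-visit summaries at V5 and V6 have no placebo group beside them. Adverse events from those four weeks all count towards V117957.

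Most efficacy outcomes are reported by the subject (void diary, PPBC, OAB-q LF, SGRA), as is the sleepiness scale (ESS). Expectation can matter for outcomes of this kind.

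**Working it through.** **1. The plan's durations reconcile.** Placebo: 2 weeks (run-in) + 2 weeks (double-blind) + 1 week (washout) = 5 weeks, as stated. V117957: 8 − 2 = 6 weeks, as stated. So each sequence has only 2 placebo weeks inside the double-blind period.

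**2. Overlap.** The minimum overlap of two 42-day courses in a 56-day block is 2 × 42 − 56 = 28 days. This does not depend on the schema's layout. With the schema's order:

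| Days | Sequence A | Sequence B | Current treatment predictable? |
|---|---|---|---|
| 1-14 (V4 at the end) | placebo | V117957 | no |
| 15-42 (V5, V6) | V117957 | V117957 | yes |
| 43-56 (V7 at the end) | V117957 | placebo | no |

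- Share of the double-blind period: 28/56 = 50%.
- Share of V117957 time: 4/6 = 67%.
- Share of double-blind placebo time: 0/2 = 0%.
- Clinic visits V4 to V7: 2 of 4.

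The table in the extracted schema is broken, so the exact switch days are inferred from the durations and the Day 14, 15, 42 and 56 columns. The visit window is ±1 day. If each of the two switches moves by 1 day, the overlap is 26 to 30 days (46% to 54%).

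**3. Which visits carry the problem into the paired contrast.**

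- V4 and V7: Sequence A gives placebo at V4 and V117957 at V7; Sequence B gives the reverse. Each subject has one value on each treatment, both from masked stretches. The bias from this mechanism at those visits is zero.
- V4 and V7 in Sequence A, V6 and V7 in Sequence B: Sequence B's V117957 value (the Day 42 diary) now comes from the predictable window, so half of the subjects are exposed.

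**4. Sensitivity for the second choice.** The method first has to reproduce the stated power. Inputs from Number of Participants: n = 38, SD of differences 1.4, difference 0.5, "using a paired t-test with a 10% one-sided significance level". The noncentrality is (0.5/1.4) × √38 = 2.20 with 37 degrees of freedom, giving power of 81.5% against the stated 81%.

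Now assume no true effect, and suppose that predictability lowers the Day 42 count by b in 19 of 38 subjects. The mean difference shifts by b/2, and the noncentrality becomes (b/2)/1.4 × √38.

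| b (assumed, per 24 h) | Shift b/2 | Shift as share of 0.5 | One-sided rejection rate |
|---|---|---|---|
| 0 | 0 | 0% | 10% |
| 0.05 | 0.025 | 5% | 12.0% |
| 0.1 | 0.05 | 10% | 14.4% |
| 0.2 | 0.1 | 20% | 19.9% |
| 0.4 | 0.2 | 40% | 34.1% |

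No value of b comes from the documents. Allowing for the extra variance when only half of the subjects are affected changes the last two rates little, to 19.8% and 33.7%.

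**The case against.** The strongest reply is that randomization assigns a sequence, and the sequence stays hidden. This stands. A reader might infer from the overlap that the blind is broken for half of the trial. The documents do not support that: knowing that everyone is on V117957 on Day 28 says nothing about who started on placebo, and Days 1-14 and 43-56 remain masked.

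A second reply is that the primary result may not be touched at all. This also stands as a condition. Section 1.4.1 names no visits, and if V4 and V7 are intended, the paired contrast avoids the window. A reader might take the higher rejection rates in the table as a consequence of the plan. They are not. They need both a V6 value for Sequence B and an assumed bias, and small assumed values give rates close to 10%.

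Third, the void counts are entered by the subject. The consent text is not among the documents, so it cannot be said that subjects know the switch days. The path from site staff to diary counts is indirect. That weakens the efficacy concern more than the adverse-event concern, where staff elicit and attribute the events.

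Fourth, 3 of each subject's 5 placebo weeks are single-blind by design (60%), so placebo weeks are not all masked either. This is correct for the whole study. The one-sidedness claimed here applies only to the double-blind weeks.

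Finally, the text supplied is largely a synopsis. Blinding procedures and analysis visits may be set out in sections not provided, so no absence of dispensing safeguards is asserted. Such safeguards would in any case not change the overlap, which follows from the durations.

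**Conclusion.** The concern holds in a limited form. For about 28 of 56 double-blind days, current treatment can be known by anyone with the schema, and there is no concurrent placebo. Within the double-blind period this falls on V117957 only: 4 of 6 weeks, against 0 of 2 placebo weeks. That rests on the stated durations and the order in the schema, with a margin of about 2 days either way for the switch days.

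The size of any resulting bias is unknown. It enters the paired efficacy contrast only if a V5 or V6 value is used. It can enter the adverse-event comparison as planned, because that comparison takes in events from the whole V117957 exposure. The stated sample size and power are not affected. This is a weakness that should be addressed, and it is inexpensive to address; it does not invalidate the design.

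**What to change.** 1. State in the protocol and the analysis plan that treatment is predictable from the schema from about Day 15 to Day 42, and that V5 and V6 have no concurrent placebo group.
2. Name the visits used in the paired efficacy comparison. Base it on V4 (Day 14) and V7 (Day 56), or pre-specify that comparison as supportive if another pair of visits stays primary.
3. Add a treatment-emergent adverse-event comparison limited to Days 1-14 and 43-56. Each subject then contributes 2 weeks on each treatment, all masked.
4. If sites do not yet hold the schema, the switch days may also be masked. Removing the sequence rows is not enough: in a crossover with one switch, a disclosed split of 6 and 2 weeks lets staff deduce weeks 3 to 6. The site-facing text would have to withhold the split and the number of switches as well, with full disclosure to the ethics committee.

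**Cost.** Items 1 to 3 need wording and one extra set of tables from data already planned. The downsides are modest. At V4, Sequence B has had only 2 weeks of V117957, against 6 weeks in Sequence A at V7. Sequence B's placebo weeks directly follow V117957, so possible carryover must be acknowledged. The restricted adverse-event comparison uses less data and should stand beside the full summary. Staff who have already read the schema cannot be re-blinded, so for them only items 1 to 3 help. No change to treatment, visits or sample size is proposed.

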**Number of Participants:**

It is estimated that up to 150 subjects will be screened to yield approximately 75 subjects that will enter Single-blind Run-in Period to yield approximately 44 subjects that will enter the Double-blind Treatment Period. A sample size of 38 completers will have 81% power to detect a treatment difference in means of numbers of micturition per 24 hours of 0.5, assuming a standard deviation of differences of 1.4, using a paired t-test with a 10% one-sided significance level. Assuming a 15% dropout rate, a sample size of 44 would be needed.

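### Is a sample size of 44 too small to give 38 completers at 15% dropout?

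*Combined protocol and SAP*

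**What the plan says.** The sample size statement is in the synopsis under Number of Participants. It starts from the number of completers: "A sample size of 38 completers will have 81% power". The inputs are a "treatment difference in means of numbers of micturition per 24 hours of 0.5", "assuming a standard deviation of differences of 1.4", and the test, "using a paired t-test with a 10% one-sided significance level". It then allows for losses: "Assuming a 15% dropout rate, a sample size of 44 would be needed".

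Earlier in the same paragraph the recruitment target is given as "approximately 44 subjects that will enter the Double-blind Treatment Period". The section states neither the formula used to allow for dropout nor a rounding rule.

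The design is a two-sequence crossover (Overall Design and Schema), so a subject with data under both treatments contributes one within-subject difference.

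**The concern.** Three linked figures sit in adjacent sentences: 38 completers, 15% dropout and 44 subjects. They do not quite fit. The usual allowance divides the number of completers by the proportion expected to complete, and the result is rounded up. That gives 45, or 46 if the two sequences are to be equal. A total of 44 is what results from multiplying by 1.15, a common error that always falls short.

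If the error were large, the trial would end with fewer pairs than its power claim assumes. The paired comparison in section 1.4.1 needs an outcome from both periods, so a subject who leaves before supplying the second outcome adds nothing to it. A sample size justification should also reproduce from its own inputs.

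**Working it through.** **Inputs**, all from Number of Participants: difference δ = 0.5 micturitions per 24 hours; SD of differences σ = 1.4; paired t-test, one-sided α = 0.10; 38 completers; 15% dropout; 44 subjects.

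**Step 1: reproduce the stated power.** For n pairs, power = P(T > t₀.₉₀,ₙ₋₁), where T is noncentral t with n − 1 degrees of freedom and noncentrality (δ/σ)√n.

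At n = 38 the noncentrality is (0.5/1.4) × √38 = 2.20 and the critical value is 1.305. Power is 81.5% (81.47% before rounding), so the stated 81% reproduces. The normal approximation gives 82.1%.

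**Step 2: the dropout allowance.**

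- Division: 38/(1 − 0.15) = 38/0.85 = 44.71, so 45 when rounded up.
- Multiplication: 38 × 1.15 = 43.7, so 44 when rounded.
- Truncating 44.71 also gives 44.
- Expected completers from 44: 44 × 0.85 = 37.4.
- Expected completers from 45: 45 × 0.85 = 38.25.
- Dropout at which 44 gives exactly 38: 1 − 38/44 = 13.6%.

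The stated figure is one subject below the exact requirement (1/44 = 2.3%), and the expected number of completers falls short by 38 − 37.4 = 0.6.

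**Step 3: what the shortfall costs.** The formula of step 1 at nearby numbers of pairs gives:

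| Pairs | Power |
|---|---|
| 36 | 79.8% |
| 37 | 80.7% |
| 37.4 (expected from 44) | 81.0% |
| 38 | 81.5% |

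At the expected 37.4 pairs, power is the 81% that the synopsis states. The loss against 38 pairs is 81.5 − 81.0 = 0.5 percentage points, or 0.8 points if 37.4 is taken down to 37.

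**Step 4: allow for chance in the number of dropouts.** Assume that each subject drops out independently with probability 0.15; the documents do not say this. With 44 randomized, the chance of 38 or more completers is 50.3%. Power averaged over the binomial number of completers is 80.9%, which again rounds to 81%. With 45 randomized, the chance of 38 or more is 63.9%.

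**The case for a change.** The best case for acting is that the sentence giving 44 presents a derived requirement and carries no qualifier, unlike the enrolment target. A requirement is rounded up, so truncating 44.71 is as much an error as multiplying by 1.15. Nor does a wish for an even total rescue 44, since the smallest even number that meets the requirement is 46. Under independent dropout, going from 44 to 46 raises the chance of at least 38 completers from about 50% to about 75%. The correction would cost one sentence.

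The arithmetic in this stands: by strict rounding up, 44 is one short. The rest carries less weight.

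- The chance of reaching 38 treats 38 as a threshold, but power changes smoothly around it and is still 80.7% at 37 pairs.
- Multiplication by 1.15 is a plausible cause and cannot be shown from the documents.
- It is too strong to say that every dropout costs a pair. The paired test in section 1.4.1 requires an outcome in both periods, and section 1.4 bases efficacy on the full analysis population, which section 1.3 defines without requiring completion. A subject who leaves during the final placebo washout or follow-up, or late in the second double-blind period, could still supply a pair. Counting all dropouts as lost pairs is therefore the cautious reading.
- Restating power as about 80% would be less accurate than the present text, because the figures at 37 and at 37.4 pairs both round to 81%.

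**Conclusion.** The concern is right on the arithmetic, but no change to the plan is needed. The stated 44 is a rounding or inflation slip of one subject, or two if equal sequences are wanted. It lowers the expected number of completers by 0.6 and power by about half a percentage point. With 44 randomized and 15% dropout, power is 81.0%, the same as the figure claimed at the precision used, and the enrolment target is in any case approximate.

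This rests on the synopsis's own difference, SD and significance level, and on the cautious reading that each dropout loses a pair. The 15% is itself a planning assumption: moving it to 13.6% removes the discrepancy altogether. Correcting the sentence would alter neither enrolment nor analysis, nor what the trial can conclude.

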**Treatment Groups and Duration:**

V117957 (6-weeks) and Placebo (5-weeks).

**Schema:**

Phase	Pre-randomization		Post-randomization										Single-blind washout	Follow-up
	Screening / washout	Single-blind Run-in	Double-blind Treatment											
Day	-42 to -16	-15	-1 A	1	14	15	28	35	42	49	56	63	70	
Clinic Visit	V1	V2	V3 A		V4		V5		V6		V7	V8	V9	
Phone call B				P1		P2		P3		P4				
Tx Sequence A		Placebo		Placebo	V117957								Placebo	
Tx Sequence B		Placebo		V117957						Placebo	Placebo			

A Visit 3, Day -1, is end of Single-blind Run-in Period and start of the Double-blind Treatment Period. At visit 3, a subject that has met all inclusion/exclusion criteria, has met all randomization eligibility criteria, and has completed all study procedures, will be dispensed double-blind study-drug with instruction to ingest first dose that evening 30 minutes before bedtime.

B Phone contact between clinic visits to assess tolerability and review diary/dosing instructions.

## 1.2. Schedule of Assessments

**Table 1. Schedule of Assessments: Pre-randomization Phase**

Period	Screening/ washout	Single-blind Run-in	
Day	-42 to -16	-15	-1
Clinic Visit A	V1	V2 B	V3
Assessment			
Informed consent	X		
Medical history	X		
Demographics	X		
Inclusion/exclusion	X	X	X
Physical exam, full	X		
Physical exam, brief		X	X
Vital signs	X	X	X
Clinical labs (chem/heme/urine)	X	X	X
Urine culture test	X	X	X
Urine drug screen	X		X
Serum pregnancy test	X		
Urine pregnancy test		X	X
12-lead ECG	X	X	X
C-SSRS	X	X	X
Concomitant medications	X	X	X
Adverse events	X	X	X
BPIC-SS C , MESA-IQ C	X	X	X
PPBC		X	X
OAB-q LF		X	X
SGRA		X	X
ESS		X	X
SISQ (diary)		Once daily, in morning	
Void Diary assessment (includes PPIUS)		During the week prior to clinic visit (V3), subject will record micturition time, type, and urgency for each episode for a minimum of 3 and up to 7-days; and will also record urine volume during 2-day weekend (or other 2-day timeframe convenient to subject work/life schedule).	
Study drug dosing (diary)		Once daily, in evening	
Diary/dosing instruction		X	X
Dispensing study drug		X	X
Drug accountability			X
OAB Symptoms characterized		X D	
Randomization criteria checklist			X
Randomization			X

ABPIC-SS= Bladder Pain/Interstitial Cystitis Symptom Score; CSSRS= Columbia-Suicide Severity Rating Scale; ECG= Electrocardiogram; ESS= Epworth Sleepiness Scale; MESA-IQ= Medical, Epidemiologic and Social Aspects of Aging incontinence questionnaire, OAB-q LF= Overactive Bladder Questionnaire long form; PPBC= Patient Perception of Bladder Condition; PPIUS= Patient Perception of Intensity of Urgency Scale; SGRA= Subject Global Response Assessment; SISQ= Symptom Impact on Sleep Questionnaire; V= Visit.

BVisit window is  $\pm 1$  day. BVisit 2, Day -15, is end of Screening/Washout Period and start of the Single-blind Run-in Period. At visit 2, a subject that has met all inclusion/exclusion criteria, has stopped their current medication treatment for OAB, and has completed all study procedures, will be dispensed single-blind study-drug with instruction to ingest first dose that evening 30 minutes before bedtime. CExclusion criteria. DSee Section 8.1.2.8; this must be completed at the clinic visit on the same day that study drug is dispensed to subject; the subject will ingest first dose of study drug that evening.

**Table 2. Schedule of Assessments: Post-randomization Phase**

*C-SSRS=Columbia-Suicide Severity Rating Scale; ECG=Electrocardiogram; ESS= Epworth Sleepiness Scale; EOS= End of Study; EOT= End of Treatment; ET= Early Termination; OAB-q LF= Overactive Bladder Questionnaire long form; P=Phone; PPBC= Patient Perception of Bladder Condition; PPIUS= Patient Perception of Intensity of Urgency Scale; SGRA=Subject Global Response Assessment; SISO= Symptom Impact on Sleep Questionnaire; V=Visit.*

A Visit window is  $\pm 1$  day.

B Visit 3, Day -1, is end of Single-blind Run-in Period and start of the Double-blind Treatment Period. At visit 3, a subject that has met all inclusion/exclusion criteria, has met all randomization eligibility criteria, and has completed all study procedures, will be dispensed double-blind study-drug with instruction to ingest first dose that evening 30 minutes before bedtime.

c May be phone call instead of clinic visit if no safety issue identified.

D Phone contact between clinic visits to assess tolerability and review diary/dosing instructions.

### 1.3. Study Population

Enrolled population: The group of subjects who sign informed consent.

Randomized safety population: The group of subjects who are randomized and receive at least 1 dose of the study drug and have at least 1 safety assessment.

Full analysis population: The group of subjects who are randomized, receive study drug, and have at least 1 valid efficacy measurement.

Per protocol population: The group of subjects who are included in the full analysis population but excluding those with major protocol deviations and those who do not receive the actual treatment they were randomized to receive.

Subjects and profiles/metrics excluded from the analysis set will be documented in the statistical analysis plan.

